4.3 Inclusion Criteria

Subjects must meet all of the following inclusion criteria to be eligible for participation in this study.

1. Verbal and written informed consent obtained from the subject
2. Males or females ≥ 21 years of age
3. Willing and able to give informed consent, comply with all study procedures, and be likely to complete the study
4. Subjects with known diagnosis of diabetic macular edema or macular edema due to retinal vein occlusion (central or branch) in the 6 weeks to 24 months prior to screening who have received at least 3 prior IVT injections of any anti-VEGF agent in the **study eye** and demonstrated a pharmacodynamic response in the **study eye** to IVT anti-VEGF treatment (aflibercept, bevacizumab, or ranibizumab) within 16 weeks of the first anti-VEGF treatment as determined by the investigator and documented by **at least 1** of the following:
 - 4a. Reduction of intraretinal/subretinal fluid by $\geq 10\%$ from the initial diagnosis as determined using SD-OCT
 - 4b. Reduction of excess CST by $\geq 10\%$ from the initial diagnosis as determined using SD-OCT (assuming nominal thickness is 300 microns)

5. Demonstrate a maintained anti-VEGF response (as determined by the investigator) compared with the initial diagnosis (prior to any anti-VEGF treatment) as assessed by SD-OCT following the most recent anti-VEGF injection (defined as reduction in central subfield thickness, intraretinal/subretinal fluid, or maintenance of a dry retina)
6. Subjects must have the most recent anti-VEGF agent administered within 42 days (6 weeks) of screening in the **study eye**.
7. Screening and baseline BCVA letter score (by ETDRS protocol) of 31 to 88 (20/240 to 20/20 Snellen equivalent)
8. If the screening and baseline BCVA letter score (by ETDRS protocol) in the **nonstudy eye** is worse than the **study eye**, the BCVA score in the **nonstudy eye** must be at least 53 letters (20/100 Snellen equivalent) or better
9. Clear ocular media and adequate pupil dilation in both eyes to permit good quality photographic imaging
10. Women of childbearing potential (ie, not postmenopausal for at least 12 months or not surgically sterile [bilateral tubal ligation, hysterectomy, or bilateral oophorectomy]) must have a negative urine pregnancy test at screening and baseline, and must use adequate birth control throughout the study if she has a nonsurgically sterile male sexual partner; adequate methods of birth control include hormonal contraceptives, intrauterine contraceptive devices, condom with spermicide, diaphragm with spermicide, and cervical cap with spermicide.

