Number of Subjects Planned: Approximately 20 subjects are planned: 10 subjects treated with 1 mg GB-102 and 10 subjects treated with 2 mg GB-102. There is no pre-set limitation on the proportion of DME or RVO subjects per dose group.

Target Population: Subjects eligible for screening must have a history of macular edema in the **study eye** secondary to DME or RVO that was diagnosed in the 6 weeks to 24 months prior to screening, treated with at least 3 prior intravitreal (IVT) injections of anti-VEGF (aflibercept, bevacizumab, or ranibizumab), and demonstrated a response anti-VEGF treatment. The most recent anti-VEGF treatment must be administered within 42 days of screening.

The investigator will interpret SD-OCT used to determine subject eligibility; there is no third-party independent reading center confirmation of any images during screening or treatment/observation.

Duration of Study Participation: Approximately 210 days (up to 30 days for screening and 180 days of treatment/observation)

Inclusion Criteria: **All Subjects (DME or RVO)**

1. Verbal and written informed consent obtained from the subject
2. Males or females ≥ 21 years of age
3. Willing and able to give informed consent, comply with all study procedures, and be likely to complete the study
4. Subjects with known diagnosis of diabetic macular edema or macular edema due to retinal vein occlusion (central or branch) in the 6 weeks to 24 months prior to screening who have received at least 3 prior IVT injections of any anti-VEGF agent in the **study eye** and demonstrated a pharmacodynamic response in the **study eye** to IVT anti-VEGF treatment (aflibercept, bevacizumab, or ranibizumab) within 16 weeks of the first anti-VEGF treatment as

determined by the investigator and documented by **at least 1** of the following:

- 4a. Reduction of intraretinal/subretinal fluid by $\geq 10\%$ from the initial diagnosis as determined using SD-OCT
- 4b. Reduction of excess CST by $\geq 10\%$ from the initial diagnosis as determined using SD-OCT (assuming nominal thickness is 300 microns)
5. Demonstrate a maintained anti-VEGF response (as determined by the investigator) compared with the initial diagnosis (prior to any anti-VEGF treatment) as assessed by SD-OCT following the most recent anti-VEGF injection (defined as reduction in central subfield thickness, intraretinal/subretinal fluid, or maintenance of a dry retina)

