5.2.2 Enrollment and Method of Assigning Subjects to Treatment Groups

This study is open-label with consecutive enrollment. When a potential subject is identified, the investigator must contact Graybug Vision's designated project manager or assigned team member managing enrollment to confirm availability for enrollment/dosing group in the study.

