## **10.2 Pretreatment Variables and Anti-VEGF History**

Pretreatment variables will include baseline BCVA and CST in the study eye. Baseline BCVA, and baseline CST will be summarized, total and by cohort, using continuous descriptive statistics. Additionally, all two pretreatment variables will be categorized as follows: SD-OCT ( $\leq 350$  and  $> 350$  micrometers), and BCVA ( $\leq 68$  versus  $> 68$  letters).

Anti-VEGF history will include previous number of Anti-VEGF injections, time (in months) since first anti-VEGF and last anti-VEGF. Number of injections will be summarized as categorical variable ( $< 5$  versus  $\geq 5$ ) and time since first and last injections will be summarized as continuous variables. All the summaries will be presented, total and by cohort.

Subject listings including all pretreatment variables and Anti-VEGF history will be provided.

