### 12.1.1 LOCF AND OBSERVED DATA APPROACH

Values and change from baseline in number of letters read correctly will be summarized using LOCF approach for study eye by visit and cohort using continuous descriptive statistics. Categorical change from baseline will also be summarized for study eye by visit, total and by cohort.

Observed values and change from baseline in number of letters read correctly will be summarized for study eye by visit and cohort using continuous descriptive statistics. Categorical changes from baseline will also be summarized for study eye by visit, total and by cohort.

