### 12.2.1 LAST OBSERVATION CARRIED FORWARD AND OBSERVED DATA APPROACH

Values and change from baseline in CST measurements will be summarized using LOCF approach for study eye by visit and cohort using continuous descriptive statistics. Categorical change from baseline will also be summarized for study eye by visit, total and by cohort.

Observed values and change from baseline in CST measurements will be summarized for study eye by visit and cohort using continuous. Categorical changes from baseline will also be summarized for study eye by visit, total and by cohort.

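### BCVA and CST change is summarized by dose with no adjustment for or stratification by baseline, although entry admits both dry and edematous eyes and acuity from 31 to 88 letters

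*Protocol*

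**What the plan says.** **Who can enter.** Criterion 5 in Protocol 4.3 is met by any of three states: "defined as reduction in central subfield thickness, intraretinal/subretinal fluid, or maintenance of a dry retina". The initial response under criterion 4b is a reduction of at least 10% in excess CST, "assuming nominal thickness is 300 microns", so most of the excess may persist. No inclusion or exclusion criterion sets a CST floor or ceiling at screening or Day 1. Criterion 7 reads "Screening and baseline BCVA letter score (by ETDRS protocol) of 31 to 88".

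**How doses are assigned.** The Protocol synopsis plans "10 subjects treated with 1 mg GB-102 and 10 subjects treated with 2 mg GB-102". Protocol 5.2.2 states: "This study is open-label with consecutive enrollment". The dosing group is confirmed with the sponsor's enrollment contact. Nothing is randomized or stratified.

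**How change is reported.** For acuity, SAP 12.1.1 says: "Values and change from baseline in number of letters read correctly will be summarized using LOCF approach for study eye by visit". For thickness, SAP 12.2.1 says: "Values and change from baseline in CST measurements will be summarized using LOCF approach for study eye by visit and cohort". The same summaries are repeated on observed data, and categorical change is added. SAP 12 provides one subgroup split, DME or RVO.

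**Where baseline appears.** SAP 8.3 defines change as the post-baseline value minus the baseline value. SAP 10.2 summarizes baseline CST and BCVA by cohort and adds that "all two pretreatment variables will be categorized as follows": CST at or below versus above 350 micrometers, and BCVA at or below versus above 68 letters. No pharmacodynamic table in SAP 15 uses these groups.

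**The concern.** What an eye can show depends on where it starts. A dry eye has little CST to lose, so holding steady is the good outcome; an edematous eye can improve by thinning. An eye entering near 88 letters can be expected to have less room to gain than one entering at 31. Subtracting baseline does not remove this dependence, because the change score itself can be correlated with the starting value.

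Entry timing widens the spread. The last anti-VEGF dose may be up to 42 days before screening, and screening is 3 to 30 days before Day 1. Day 1 can therefore fall from about 3 to 72 days (42 + 30) after that dose.

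Two things are at stake for the secondary objective. First, the 1 mg and 2 mg columns may differ because the groups enrolled different eyes. Second, the mean within either column depends on how many dry eyes it holds, so a treatment that dries edematous eyes and maintains dry ones can show a modest average. The unadjusted FAS tables (14.2.1.1, 14.2.1.5, 14.2.2.1 and 14.2.2.5) are marked for topline delivery, so these columns will be read early and side by side.

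**Working it through.** **1. The plan's own figure.** Protocol 9.4 says adverse event rates above 15% overall and 30% per dose are detectable with about 95% confidence. The rule of three gives 3/20 = 15% and 3/10 = 30%. Exact chances of at least one event are 1 - 0.85^20 = 0.961 and 1 - 0.70^10 = 0.972. The figure reproduces, but it concerns adverse events only. The documents give no SD, correlation or precision for CST or BCVA.

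**2. Inputs.** From the documents: 10 eyes per dose. Assumed: baseline CST SD 60 to 140 micrometers; slope of change on baseline -0.3 to -0.7; for BCVA, SD 8 to 15 letters and slope -0.2 to -0.5. All shifts below are absolute sizes.

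**3. Chance imbalance on a continuous scale.** SE of the baseline difference = SD × sqrt(2/10). Shift in the difference in mean change = |slope| × baseline difference, with identical drug effect.
- SD 60: SE 26.8; at slope 0.3 the shift is 8.0 micrometers.
- SD 100: SE 44.7; at slope 0.5 the shift is 22.4, with a 95% range of ±1.96 × 22.4 = ±43.8.
- SD 140: SE 62.6; at slope 0.7 the shift is 43.8.
- BCVA: 8 × 0.447 × 0.2 = 0.7 letters, up to 15 × 0.447 × 0.5 = 3.4 letters.

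**4. The same question as a mix of eyes.** Suppose edematous eyes change by -60 and dry eyes by +10 micrometers at either dose.
- 3 dry of 10: (3 × 10 + 7 × (-60))/10 = -39.
- 7 dry of 10: (7 × 10 + 3 × (-60))/10 = -11.

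The columns differ by 28 micrometers with no dose effect.

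**5. How often would such splits arise?** With K edematous eyes among 20 and a split as good as random, the chance of x in one group is C(K,x) × C(20-K,10-x) / C(20,10).
- K = 6, 8 or 10: the groups differ by at least 2 edematous eyes with probability 0.63, 0.65 or 0.66.
- They differ by at least 4 with probability 0.14, 0.17 or 0.18.

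The 3-versus-7 example is a 4-eye difference, so it is an uncommon but ordinary chance result. A 2-eye difference moves the contrast by 2/10 of the gap in mean change between the two kinds of eye: 10, 20 or 30 micrometers for an assumed gap of 50, 100 or 150.

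**6. What adjustment would buy.** With equal variances at baseline and follow-up and correlation r, the slope of change on baseline is r - 1. The adjusted variance of the dose contrast is (1 + r)/2 of the change-score variance: 65%, 75% or 85% at r = 0.3, 0.5 or 0.7, before a small loss of degrees of freedom. At SD 100 and r = 0.5, the SD of change is 100 × sqrt(2 × 0.5) = 100, so the SE of the raw contrast is 44.7. The baseline part is (22.4/44.7)² = 25% of that variance.

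**The case against.** The strongest reply is that the plan makes no dose comparison. The study is uncontrolled and descriptive, safety is primary, and no between-dose estimate, interval or test of CST or BCVA is planned. That limits the severity. It does not stop a reader from comparing adjacent topline columns, and it does not address the blending within each column.

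A reader might infer that the plan ignores baseline or reports only raw means. The documents do not support that. Baseline is subtracted, tabulated by cohort (Table 14.1.2.1, also topline) and cut into groups. Medians, ranges, categorical change and by-diagnosis tables are planned. What is missing is any pharmacodynamic summary adjusted for or stratified by baseline. The baseline table can reveal an imbalance, but not how far it moved the change columns.

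A reader might also infer that the dose columns are biased, by 8 to 44 micrometers. That does not follow either. The figure rests wholly on assumed inputs and describes chance imbalance. Step 6 shows that this component is already inside the spread of the change scores; it is not an extra error. Non-random assignment could produce a larger imbalance, but the documents do not show that it does.

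Two further points stand in part. Maintenance is captured elsewhere, through rescue-free status and Kaplan-Meier time to first rescue, so a stable dry eye is not lost from the study's evidence; it is only obscured in the CST and BCVA means. Subject listings would let a reader pair baseline with follow-up by hand, and SAP 1 allows supplementary analyses, but neither prespecifies the display.

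Finally, floor and ceiling effects are not linear, so a common-slope model handles them imperfectly and cannot remove other confounding. This is why the grouped displays and plots should lead and the adjusted mean should be a supplement.

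**Conclusion.** The concern holds in a limited form. Entry allows a wide range of starting states, assignment is not randomized, and no BCVA or CST change summary is adjusted for or stratified by baseline, although suitable groups are already defined. The change columns can therefore partly reflect baseline mix; the documents do not establish that they will.

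The size is unknown. It is about 8 to 44 micrometers of CST per one-standard-error imbalance, and about 0.7 to 3.4 letters of BCVA, under the assumed SDs and slopes and a split as good as random. It affects the reading of secondary, descriptive endpoints. It does not touch the primary safety analysis or the sample size statement, and it is not a fault in criterion 5, which is a legitimate choice for previously treated responders. A modest change to the SAP is worth making.

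**What to change.** In SAP 12.1.1 and 12.2.1, with Tables 14.2.1.x and 14.2.2.x, keep the unadjusted summaries and add:

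1. Observed and LOCF change by the SAP 10.2 baseline groups (CST at or below versus above 350 micrometers; BCVA at or below versus above 68 letters), by dose and in total. State that the CST cut only approximates dry versus edematous, since criterion 4b takes 300 micrometers as nominal.
2. Plots of each eye's baseline against its change, marked by dose, added to the figure list in SAP 17.
3. As a descriptive supplement, the baseline-adjusted mean change per dose (ANCOVA on the eye's own baseline value) with 95% CI and no test. Label it as assuming a common linear slope and as not a randomized dose comparison.

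The cost is SAP wording, some table columns and a few figures. No new data, visits or eligibility changes are needed. The downside is small cells: about 5 eyes per dose in each group if the split is even, and fewer if it is not. The individual plots are there for that reason, and the baseline groups should not be crossed with diagnosis as well.

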4.4 Exclusion Criteria

1. History, within 6 months prior to screening, of any of the following: myocardial infarction, any cardiac event requiring hospitalization, treatment for acute congestive heart failure, transient ischemic attack, or stroke
2. Uncontrolled hypertension with systolic blood pressure ≥ 160 mmHg and/or diastolic blood pressure ≥ 95 mmHg at the Screening Visit
3. Uncontrolled diabetes mellitus, defined as hemoglobin A1c $>12.0\%$ at the Screening Visit
4. Chronic renal disease requiring chronic hemodialysis or renal transplantation
5. Participation in any investigational study within 30 days prior to screening, or planned use of an investigational product or device during the study; any exposure to a prior investigational drug product must be fully washed out (at least 5 half-lives)
6. Previous participation in an investigational study of GB-102
7. Spherical equivalent of the refractive error in the **study eye** demonstrating more than -6 diopters of myopia (prior to cataract or refractive surgery) at the Screening Visit
8. Uncontrolled IOP, defined as an IOP > 25 mmHg, despite antiglaucoma medications in the **study eye** at the time of screening or controlled glaucoma that requires management with > 2 topical hypotensive medications

9. Presence of any clinically significant epiretinal membrane or vitreomacular traction in the **study eye**
10. History or evidence of any of the following in the **study eye**:
 - a. Macular surgery or other surgical intervention for AMD
 - b. Prior retinal detachment
 - c. Vitrectomy
 - d. Retinal laser treatment with the exception of prior laser photocoagulation for treatment of diabetic retinopathy
 - e. Glaucoma filtering surgery (eg, trabeculectomy) or glaucoma drainage device (eg, Ahmed valve or Baerveldt valve) including minimally invasive glaucoma shunts (eg, minimally invasive glaucoma surgery) prior to the Screening Visit. Selective laser trabeculoplasty (SLT) ≥ 3 months prior to Screening Visit is allowed.
 - f. Cataract surgery within the 3 months prior to the Screening Visit
 - g. Neodymium:yttrium-aluminum-garnet (Nd:YAG) laser capsulotomy within the 30 days prior to the Screening Visit. Note: prior Nd:YAG laser posterior capsulotomy in association with a posterior intraocular lens implantation is allowed.
 - h. Corneal refractive procedures (laser-assisted *in situ* keratomileusis [LASIK] or photorefractive keratectomy) within the 6 months prior to the Screening Visit or planned during the study
 - i. Corneal transplantation surgery
 - j. History of advanced glaucoma with visual field loss encroaching on central fixation
 - k. Intravitreal steroid injection (eg, triamcinolone suspension) within the past 3 months, bioabsorbable steroid implant (eg, Ozurdex[®]) within the past 12 months, and/or presence of any steroid implant in the study eye (eg, Iluvien[®] or Ozurdex[®]) at the time of the Screening Visit
 - l. Active retinal or iris neovascularization in the study eye
11. Anterior chamber intraocular lens, aphakia, or violation of the posterior capsule in the **study eye**
12. History or clinical evidence of other concurrent conditions deemed by the investigator to likely impact the subject's clinical safety or to interfere with the interpretation of the study results including, but not limited to:
 - a. Proliferative diabetic retinopathy in the study eye
 - b. Choroidal neovascular lesion secondary to wet AMD in the study eye
 - c. Any retinal or choroidal vasculopathy, other than due to diabetes or retinal vein occlusion in the study eye

- d. Inflammatory conditions of the anterior or posterior segment (eg, chronic keratoconjunctivitis, uveitis, retinal vasculitis, neuritis, iritis, scleritis, or blepharitis) in the study eye
 - e. Subfoveal involvement by any of the following: fibrosis, serous pigmented epithelial detachment, retinal pigmented epithelial tear, or geographic atrophy in the study eye
 - f. Subfoveal hemorrhage that is ≥ 1 disc areas in size in the study eye
 - g. Any media opacity that prevents proper visualization of the fundus and/or adversely alters visual acuity, in the opinion of the investigator in the study eye
 - h. Prior radiation therapy in the region of the eyes
 - i. History of demyelinating disease (eg, multiple sclerosis, neuromyelitis optica), optic neuropathy, and/or optic neuritis.
13. Any bacterial, viral, fungal, or parasitic infection in either eye within the 30 days prior to the Screening Visit
14. Known allergy to constituents of the study drug formulation, ocular antimicrobicide solutions, or clinically relevant hypersensitivity to fluorescein
15. Women who are pregnant or lactating
16. Men who are unwilling to practice 2 measures of adequate contraception (if having sexual intercourse with a woman of child-bearing potential) or who desire to donate sperm during the time from first dose of study drug until exiting the study. If a male exits the study early and wants to donate sperm, a minimum wait period of 12 weeks following the last dose of study drug is required.
17. Presence of any other concurrent medical or social condition deemed by the investigator to likely interfere with a subject's ability to provide informed consent, comply with the study visits and assessments, or interfere with the interpretation of study results
18. Prior exposure to oral sunitinib malate in the past 6 weeks

5 INVESTIGATIONAL PRODUCTS

5.1 Study Drug and Administration

5.1.1 Investigational Product (GB-102)

GB-102 is a depot formulation of sunitinib malate intended for IVT injection.

The formulation consists of microparticles made from PLGA and mPEG-PLGA. The mPEG component provides a hydrophilic, biocompatible property. During production, the microparticles are surface treated to facilitate their aggregation upon IVT injection to form an implant-like depot in the vitreous. After IVT injection, the microparticles degrade into lactic acid, glycolic acid, and mPEG. GB-102 microparticles are approximately 25 μm in diameter, which allows IVT delivery in a 50- μL injection using a 27 G thin-walled needle in the inferior *pars plana* (6 o'clock region). The mPEG surface treatment of the microparticles facilitates aggregation into a single bioabsorbable, implant-like depot following IVT injection. This delivery method allows the microparticles to assume residence in the inferior portion of the posterior segment, away from the visual axis. The depot slowly biodegrades over 4 to 6 months. Because the released sunitinib avidly binds to ocular melanin, the RPE serves as a secondary drug reservoir to maintain therapeutic levels of sunitinib even though the depot is fully resorbed.

5.1.2 Study Drug Administration

Each study center will have a trained, technician who will prepare the study drug syringes for IVT injection. The Sponsor will provide the necessary training and all supplies required for the reconstitution of study drug, including vials containing lyophilized GB-102 dry powder, pre-filled syringe with hyaluronic acid, needles, and syringes.

Rescue medication allowed is any anti-VEGF (aflibercept, bevacizumab, or ranibizumab) and should be used in accordance with the sites standard practice in administering these agents for the treatment of DME or RVO. The Sponsor will not supply rescue medication.

Adequate anesthesia and eye preparation materials (eg, povidone iodine solution) will be given prior to the IVT injection per the injecting investigator's standard-of-care. IOP measurement will be obtained before the injection at Baseline (Day 1). The investigational product, regardless of concentration, should be prepared and administered as follows in the study:

GB-102: Reconstituted drug will be administered via IVT injection using a 1-cc tuberculin Luer Lock syringe with a 27 G thin-walled needle.

